2.4 Potential Risks & Benefits

2.4.1 Known Potential Risks

Risks are as follows: a) Participants could develop mild to moderate emotional discomfort or frustration associated with psychiatric interviewing or filling out questionnaires; b) participants may experience subjective distress during treatment; c) potential side effects of E2 include headache, breast pain, irregular vaginal bleeding, stomach cramps, nausea, or hair loss. These side effects, however, are documented with the long-term use of E2 and there are no known side effects of short-term use of E2 as proposed in this application; e) noise from the fMRI machine can cause discomfort. Participants will be wearing earplugs to minimize this discomfort and they can stop the study at any time; f) the electrical shock will be applied to the foot and is uncomfortable but not painful but may cause discomfort in the participants; g) participants may find blood withdrawal at different time points discomforting or slightly painful; h) the association between the electric shocks and the pictures to be presented during the fear conditioning and extinction paradigm might induce some anxiety when viewing the pictures in anticipation of the shock.

It is anticipated that subjects with derive benefit from receiving well-delivered treatment for PTSD. The findings from these studies will help to advance psychiatric research generally, and knowledge of the role of estrogen in augmenting existing treatments for PTSD. Results of this study will also help us to identify important information regarding fear extinction and learning, which could advance clinical knowledge of anxiety disorders. By addressing these important questions, the findings from the proposed study will help shape further research on fear extinction, thereby improving our understanding of fear learning.

2.4.2 Known Potential Benefits

Participants may not directly benefit as a result of participating in this study. Participants may benefit from receiving careful diagnostic assessment, clinical monitoring and well-delivered first line evidence based targeted psychotherapy treatment for PTSD. Participants may also benefit from knowing that they have contributed to the scientific understanding of the role of estrogen in augmenting existing treatments for PTSD and that this may help other women with similar problems. The data to be ascertained will contribute to enhancing our knowledge of PTSD psychopathology and the neural mechanisms associated with treatment outcomes in PTSD.

3 Objectives and Purpose

In this proposal we will examine the mechanisms by which estradiol (E2) administration in conjunction with Prolonged Exposure therapy (PE) could enhance extinction recall and activation of the extinction network in individuals with significant PTSD symptoms; and to examine how such an enhancement may be associated with PTSD symptom reduction

3.1 Primary Objective

The primary objective is to delineate the influence of exogenous administration of estrogen on conditioned responses during extinction recall in women with PTSD.

Specific Aim 1.1: To examine the effects of E2+PE on the extinction-induced psychophysiological responses (SCR), neural responses, and the information flow between the fear extinction nodes at post-PE sessions relative to pre-PE.

Hypothesis 1.1: During extinction recall, both groups will show lower SCR at post- relative to pre-PE. A general improvement is expected over time in both groups given the anticipated benefits of PE alone. However, we expect a significant Time x Group interaction, where the Estradiol-treated group should exhibit significantly lower fear levels (indexed via SCR) at the follow-up assessment relative to the Placebo group. 2) For both groups, extinction recall-induced activations will be higher in brain regions associated with extinction learning and recall (i.e. vmPFC and hippocampus) and lower in regions associated with fear expression (i.e. dACC and amygdala) at post- relative to pre-treatment. Note that a general improvement from pre to post is expected in both groups, given the anticipated benefits of PE alone. We do expect, however, a significant

Time x Group interaction, with most pronounced effects at post-PE in the estradiol-treated group. 3) Information flow between the extinction nodes will improve (indexed by DCM models), with stronger effects in E2+PE after treatment.

Specific Aim 2: To examine the impact of E2 administration on PE efficacy at reducing PTSD symptom severity.

Hypothesis 2: PTSD symptom severity will be significantly lower in the E2+PE group relative to the Placebo+PE group following acute treatment, as well as at the 3- and 6-month follow-up assessments.

Specific Aim 3: To test the interaction between E2+PE induced psychophysiological and neuronal changes (pre-to-post) with the improvement of PTSD symptom severity.

Hypothesis 3: PTSD symptom reduction will correlate with BOLD and SCR changes observed during extinction recall following PE.

4 Study Design and Endpoints

Section 4 will provide a brief overview of the phases of the clinical protocol (screening, baseline, experimental days). More details on procedures occurring during each phase will be included in subsequent sections of the protocol.

Therapist Training Procedures:

In addition, prior to beginning work with randomized study participants as an approved study therapist, all study therapists at UTHealth Houston will undergo a training procedure with a study participant recruited to participate in this training phase of the study. The details of this are outlined in 7.3.1. and a separate consent form explaining the training procedures with the treatment but not imaging components of the study is included.

4.1 Description of Study Design

This is a randomized, double-blind, placebo-controlled trial where 80 participants will undergo fear conditioning, fear extinction, and fear recall experiments, fMRI scans, as well as receive Prolonged Exposure treatment. Participants will be randomly assigned to additionally receive a pill placebo or 2 mg Estradiol.

The study includes a) Psychiatric intake evaluation to determine study eligibility, b) 2 consecutive day visits that occur at visits 2 and 3 and again at visits 10 and 11 with fMRI scanning on the second day, c) prolonged exposure therapy sessions. The 4 consecutive visits include roughly 1 hour fMRI scans, as well as fear conditioning through a mild shock stimulus from a battery-powered stimulator, the Biopac STM100C Stimulator, and the use of psychophysiological measures (SCR). There are clinical follow up assessments at 3 and 6 months post treatment.

4.2 Study Endpoints

4.2.1 Primary Study Endpoints

Primary study endpoint will be Blood Oxygen Level Dependent BOLD fMRI signals and Skin Conductance Response (SCR) during recall.

4.2.2 Secondary Study Endpoints

The secondary study endpoint will be the evaluation of PTSD symptom severity using DSM-5 PTSD symptoms measured with the Clinician-Administered PTSD Scale for DSM-5 (CAPS) Past Week version at the Post-treatment assessment. In addition to the experimental primary and secondary end points, there will be primary safety endpoints. Subjects will not receive any stimulation beyond what they consider highly annoying to them. Subjects will be thoroughly screened prior to starting the fMRI component of the study to make sure that they have no metal implants of any kind that would be considered a hazard to their health in the fMRI. We will use a metal detector to screen all subjects and make sure that they carry no metals to the

scanner room. Pregnancy tests will be done for all female participants with child-bearing potential prior to the initiation of the experiment to rule out pregnancy. If pregnancy is suspected, subjects will not be allowed to participate in the study. If any excess movement by the subjects is observed (which could be indicative of discomfort), the study staff will check with the subjects and inquire whether they would like to stop the experiment. After estrogen administration, all subjects will be monitored for any adverse events. This risk, however, is low given that estrogen is a commonly used agent with known side effect profiles, a component of many oral and non-oral birth controls and given only for 5 total 2mg/ dose twice weekly doses in the study. Reasons for study discontinuation for any participants who stop the treatments or study prematurely will also be recorded and reported.

5 Study Enrollment and Withdrawal

5.1 Inclusion Criteria

In order to be eligible to participate in this study, an individual must meet all of the following criteria:

1. Female, 18-45 years of age
2. Chronic (at least one month post-trauma) DSM-5 FULL PTSD diagnosis **OR subPTSD** diagnosis (subPTSD defined as: meeting criterion A, F, G, H, and clusters B, C, and at least 1 of the clusters D or E.)
3. CAPS-5 Past Month score ≥ 20
4. Criterion A traumatic event
5. Stable medications for 3 or more months by the time of study entrance (with the exception of benzodiazepines)
6. Women on oral contraceptives, specifically those using monophasic or biphasic of first, second, third or fourth generation with up to 35mcg of ethinyl estradiol; OR using etonogestrel / ethinyl estradiol 0.120mg/0.015mg per day vaginal ring birth control; OR using the norelgestromin / ethinyl estradiol 0.150mg/0.035mg per day transdermal patch birth control.
7. Willing and able to provide informed consent

5.2 Exclusion Criteria

An individual who meets any of the following criteria will be excluded from participation in this study:

1. Diagnosis of bipolar I disorder with a past year manic episode
2. Diagnosis of a psychotic disorder or psychotic symptoms that would interfere with the ability to focus on posttraumatic stress disorder (PTSD) in clinic, as determined by clinical judgment.
3. Diagnosis of moderate or severe substance use disorder that would interfere with the ability to focus on posttraumatic stress disorder (PTSD) in clinic, as determined by clinical judgment.
4. Cognitive impairment that would interfere with the ability to focus on posttraumatic stress disorder (PTSD) in clinic, as determined by clinical judgment.
5. History of neurological disease (that involves the brain), seizure, or significant head trauma (i.e., extended loss of consciousness, neurological sequelae, or known structural brain lesion).
6. Suicidal ideation with imminent risk that warrants a higher level of care.
7. Concurrent trauma focused psychotherapy
8. Pregnancy (to be ruled out by urine β -HCG).
9. Metallic implants or devices contraindicating magnetic resonance imaging by interfering with patient safety or fMRI data collection. Cases will be cleared by the Principal Investigator and/or Baylor College of Medicine (Imaging).
10. History of breast cancer or hormone-responsive cancer.
11. Use of benzodiazepines
12. Self-injurious behavior that involves suicidal intent, requires medical attention, or occurs daily.
13. High risk of adverse emotional or behavioral reaction, and/or an inability to understand study procedures or the informed consent process, based on investigator/clinician clinical evaluation (e.g., evidence of serious personality disorder, antisocial behavior, serious current stressors, lack of meaningful social support)

5.3 Vulnerable Subjects

This study does not involve the enrollment of pregnant women, prisoners, employees, people with cognitive impairment or any decisional incapacity, fetuses, neonates or elderly or children under the age of 18.

Confidentiality for all study participants will be strictly adhered to. Only group level de-identified outcomes will be shared outside the study team and UTHealth Houston approved functions with access to clinical research participant level data (e.g. IRB, UTHealth Houston research pharmacy). All participants will undergo formal informed consenting in person (or online via Redcap) with an IRB approved clinical study investigator with as much time for questions as needed.

5.4 Strategies for Recruitment and Retention

Subjects will be recruited from the local community via advertisement as well as social media such as: Craigslist, Reddit, Instagram, LinkedIn, Twitter, Facebook, Research Match, and Nextdoor, as well as UTHealth Houston's MyChart, and BuildClinical. Research Match is a nonprofit program funded by the NIH that connects people interested in participating in research studies with applicable studies. It will specify location, the study's inclusion criteria, and be linked with the approved prescreen. BuildClinical is a data-driven software platform that helps academic researchers recruit participants for research studies more efficiently using social media, software, and machine learning. They have worked with IRBs in the US to ensure they adhere to all the appropriate guidelines and procedures. They utilize study-specific advertisements to engage participants on digital platforms such as Facebook, Google, WebMD, etc., and redirect them to a study-specific landing page should they click it. On the landing page, the person can complete an online pre-screen questionnaire that gets routed into BuildClinical's platform. BuildClinical's Secure Socket Layer (SSL) software, which encrypts all inputted information, keeps subject information private and HIPAA compliant. Their backend servers are stored in the USA at some of the most secure data centers in the world.

The study team will work with the UTHealth Houston communications department to create a webpage describing our research study on the websites that the institution uses to recruit participants for studies and will work with UTHealth Houston's MyChart to recruit from UTHealth Houston patients. In addition, we will post flyers at UTHealth locations, show ads on the internal UTHealth Houston tv monitors, and use UTHealth Houston's website and newsletters.

Subjects will also be recruited from the public through local media advertisements and UTHealth Houston clinical sites, including Behavioral Sciences Research Institute registry/recruitment (BSRI). We will approach patients in clinic, via posted flyers in the outpatient buildings, post signs on campus, and we will also recruit from the Department of Psychiatry Recruitment Registry: HSC-MS-23-0768. Flyers will be posted at local university campuses, hospitals, and community clinics. Local advertising efforts will instruct prospective participants to complete a brief online confidential screening questionnaire. The Research Assistant, or study team member, at UTHealth Houston will then call and screen individuals for eligibility based on results of the screening questionnaire. Individuals who contact our centers will be screened initially by phone for interest in the proposed research, as well as general diagnostic and study eligibility, and interest and availability for research study participation. Such screening is routine at UTHealth Houston and requires about 30 minutes. Callers who meet initial potential eligibility based on the phone screen will be scheduled for an in-person assessment with a study clinician. At this visit they will review and sign the informed consent form (if not already consented online via Redcap), and assessments will occur to determine their final eligibility for the study.

There is a plan for sharing contact information of the previously consented participants interested in future research studies. We will share a list of participant contact information (name, email and phone number) to [name] team through a secure process (i.e., OneDrive) for the study HSC-MS-23-1106.

Communicating with the Research Team: We added the following information to our informed consent, regarding texting research participants and give participants the option to opt in or out of receiving text communications from the research team.

5.4.1 Use of MyChart for Recruitment Purposes

The study will also use UTHealth Houston's MyChart to identify subjects. Data gathered will be used to identify potentially eligible subjects who did not opt out of being contacted for research. We will also use this data to gain contact information about the patient.

A research coordinator, or study team member, will contact potential participants identified through MyChart. Any recruitment information containing sensitive information will be sent by secure email (e.g., Send Safe) email or will be done through MyChart. Once contact is made, approved recruitment language will be used to communicate the reason for contact and subjects will be asked if they are interested in participating in this specific study. If the potential subjects agree, the study team will provide the potential participants with information regarding the next steps for participation. If a subject requests information regarding opting out of further recruitment for all research, subjects will be directed to contact the UTHealth Houston department/contact that is responsible for processing such requests.

5.5 Duration of Study Participation

We will ask participants to make 14 visits to our facilities at UTHealth Houston. After the first assessment visit, participants will go through the 2-day visit for the emotional learning task. Following this, the participants will go through 6 therapy sessions over 3 weeks: 2 sessions per week. On visits 10 and 11 participants will go through the emotional learning task again and complete clinical outcomes assessments. Participants will return at 3 and 6 months for follow ups.

5.6 Total Number of Participants and Sites

Recruitment will end when approximately 80 subjects complete the screening, meet eligibility criteria and are randomized. It is expected that approximately 80 subjects will be randomized between both UTHealth Houston and Penn.

5.7 Participant Withdrawal or Termination

5.7.1 Reasons for Withdrawal or Termination

Participants are informed they are free to withdraw from participation in the study at any time upon request. Patients' participation in the treatment trial may be discontinued at any time because of serious medication side effects or if continued participation is considered a danger to their welfare. Specific reasons for treatment discontinuation include: 1) Serious adverse event; 2) Extreme laboratory values confirmed with a repeat test; 3) discontinuation would be in the patient's best interest; 4) Participant no longer wants to continue.

5.7.2 Handling of Participant Withdrawals or Termination

Participants deemed to be candidates for discontinuation will be reviewed by the principal investigator and other relevant project personnel (e.g., study psychiatrist or study treatment provider). Patients who require discontinuation of study treatments for any reason will be scheduled for a final evaluation and given appropriate treatment referrals. The reason patients are discontinued from the clinical trial will be clearly specified.

6 Study Drug and Procedural Intervention

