In addition, any participants who have not improved at least 30% from their pre-treatment the 3-month follow-up CAPS-5 Past Week score and have a CAPS-5 Past Week score of 26 or greater at the 3-month follow-up will be offered additional treatment if they wish. Participants will then have the option to receive up to 4 additional sessions of PE delivered for an hour a week (for a total number of 10 sessions of PE) immediately following the 3-month follow-up visit. All participants will receive safety assessments throughout the study and at 3 and 6 month follow ups, and will be assisted with clinical referrals if desired and/or indicated.

Monitoring of Mental Status and Mood. Subjects' mental status will be closely monitored throughout the course of the study. As previously stated, it is not uncommon for treatment of trauma-related symptoms to be associated with temporary exacerbation in participants' symptoms of PTSD and depression. However, some participants may experience symptom exacerbations or psychiatric emergencies that require treatment beyond that provided by the study. In all cases, the client's mental status will be the utmost priority and immediate action will be taken to provide appropriate care. The intake evaluation for the study will include the Columbia-Suicide Severity Rating Scale to adequately assess suicide risk before study enrollment, and study therapists will routinely evaluate mood over the course of treatment, including the presence or absence of suicidal thoughts (using the BDI-II followed by clinical interview with a modified suicide check list at each

visit), and if any suicidal thoughts, plans or actions are present, these will be dealt with using the detailed plan outlined in Protection against Suicidality in the section immediately below.

Management of Suicide Risk

Several strategies will be implemented to assist in early identification and appropriate management of suicide risk. This protocol will utilize the Columbia Suicide Scale (C-SSRS) at screening and a suicide check list at each clinical and psychiatric assessment follow up visit to routinely assess suicidal ideation, impulses and behaviors. In addition, the BDI will be completed and reviewed by the study therapist who will be working closely with each participant.

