Minimizing risk during fMRI. No subjects will have metallic implants contraindicating MRI. All female subjects will have pregnancy ruled out via a urine pregnancy (beta-HCG) test. Subjects may ask to have a scan stopped and discontinue participation in the study at any time. Every effort will be made to reassure the patient and minimize any discomforts while in the fMRI scanner. Subjects will be able to converse with a staff member via a microphone and speaker system throughout. To reduce the discomfort caused by the MRI loud noises, subjects will wear earphones to enable presentation of auditory stimuli while minimizing ambient scanner noise.

Participant Study Discontinuation

Participants are free to discontinue study treatments or assessments at any time.

An individual patient's participation in the treatment trial may be discontinued at any time because of serious medication and/or therapy side effects or if continued participation is considered a danger to their welfare.

Patients who require discontinuation of both of the study treatments (PE and double blind Estrace) for any reason will be scheduled for a final evaluation and given appropriate treatment referrals. The reason the patients are discontinued from the clinical trial and any referrals made will be clearly specified.

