9.3 Analysis Datasets

The proposed experiments in this project are aimed to examine the effects of E2+PE on the extinction-induced SCR and neural responses at post-PE sessions relative to pre-PE. SCR will be recorded as a psychophysiological index of fear extinction and extinction recall. We will conduct standard fMRI analyses to examine information flow changes in the extinction network. These data will test hypothesis 1 stated above.

Another objective of the project is to examine the impact of E2 administration on PE efficacy at reducing PTSD symptom severity. Here, we will use all clinical data (CAPS) before and after treatment as well as 3, 6 months follow up data. These data will be used to test hypothesis 2 stated above.

The combined data sets will then be used to test hypothesis 3 above.

Primary analyses will be based on a modified intent to treat sample including all participants who took at least one dose of the study medication.

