9.4.6 Baseline Descriptive Statistics

We will perform descriptive statistics prior to testing our hypotheses. These statistics will include means (or frequencies and proportions for categorical variables), standard deviations, skewness and kurtosis, and odds-ratios. Variables with distributions violating assumptions of normality will be transformed. If this fails to improve the normality of the distribution, distribution-free statistics will be employed. This study has baseline, post-treatment, and two follow-up assessments, creating clustered data due to repeated measures. Thus, we will use established methods for such study designs to examine treatment differences, including the two most popular approaches for longitudinal data modeling: the generalized estimating equations (GEE) and linear mixed-effects model approach (LMM). We will apply these models for both the intent-to-treat and completer analyses. Inference based on GEE or LMM is valid provided that missing data are non-informative or "missingness" does not depend on the value of the unobserved outcome. Although missing data in many studies in mental health research are non-informative, we will perform sensitivity analyses to ensure that this is the case. In particular, we will entertain both parametric and semi-parametric models that assume some missingness mechanism and compare estimates obtained from such models with those from GEE and LMM. Such analyses will inform us whether the non-informative missingness assumption is violated and if so, to what extent. If the non-informative missingness assumption is deemed to be severely violated, we will report treatment effects using the methods that account for informative missingness.

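### Section 5.7.2 handles stopping study treatment as leaving the trial and provides no continued outcome collection, although the primary sample includes everyone who took a dose

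*Combined protocol and SAP*

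**What the plan says.** **Handling of stoppers.** Section 5.7.2: "Patients who require discontinuation of study treatments for any reason will be scheduled for a final evaluation and given appropriate treatment referrals". The following sentence reads: "The reason patients are discontinued from the clinical trial will be clearly specified".

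**Parallel rule.** Section 8.1, under participant study discontinuation, is narrower: "Patients who require discontinuation of both of the study treatments (PE and double blind Estrace) for any reason will be scheduled for a final evaluation". The same part of 8.1 says: "Participants are free to discontinue study treatments or assessments at any time".

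**Analysis set.** Section 9.3, repeated in 6.1.7: "Primary analyses will be based on a modified intent to treat sample including all participants who took at least one dose of the study medication".

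**Other text that bears on the point.** Section 4.2.2: "Reasons for study discontinuation for any participants who stop the treatments or study prematurely will also be recorded and reported". Section 8.1: "All participants will receive safety assessments throughout the study and at 3 and 6 month follow ups". Section 9.4.6 plans GEE and mixed models for intent-to-treat and completer analyses, with sensitivity analyses for missing data, and concedes: "Inference based on GEE or LMM is valid provided that missing data are non-informative".

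**The concern.** Stopping a treatment and leaving a study are different events. An analysis of everyone dosed needs outcomes from everyone dosed, including those who stopped capsules or therapy early. Section 5.7.2 runs the two events together, and other text follows the same pattern. Section 5.7.1 moves from ending participation in the trial to reasons for ending treatment as if they were one thing. Sections 8.1 and 9.4.4 frame the decision after a side effect as whether the participant should stop taking part in the study.

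If sites follow this as written, a participant who stops after a few sessions has one undefined evaluation and is gone. Her post-treatment scan, skin conductance and CAPS-5 cannot be recovered later. Those who stop because of side effects or another reason listed in 5.7.1 may differ from those who finish, and may differ by arm. The modified intent-to-treat analysis would then rest largely on completers plus an assumption about the rest.

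The different triggers in 5.7.2 and 8.1 add a second problem. A participant who stops capsules but continues PE falls under the first rule on one reading and outside the second, so the two sites could handle her differently.

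**Working it through.** **1. Where the post-treatment endpoints come from** (Schematic of Study Design; Section 7.3, Tables 1 and 2)

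| Endpoint | Baseline | Post-treatment |
|---|---|---|
| SCR and BOLD at extinction recall (primary) | Visit 3 | Visit 11, after conditioning and extinction at Visit 10 |
| CAPS-5 Past Week (secondary) | Visit 1 | Visits 12, 13, 14 |

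No CAPS-5 is scheduled during therapy. PDS-5 is taken at each session, but it is not the stated endpoint. A stopper who is not seen at Visits 10-14 therefore has no post-treatment primary value and only a pre-treatment CAPS-5, unless the final evaluation happens to include one.

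**2. Whether a stopper has a dated route to those visits**

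- Section 7: treatment visits are windowed from the previous visit.
- Section 7.1.2: the second experimental block follows completion of the six PE sessions.
- Schematic: Visit 12 is timed from Visit 11.
- Section 4.1: follow-ups are counted from treatment.

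Each date hangs on the one before it. None is defined for someone who stops after, say, session 3.

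**3. The plan's own figure** (Section 9.5: 80 patients, about 20% dropout, about 20% unusable data, full data expected from 50)

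- Multiplicative: 80 × (1 − 0.20) × (1 − 0.20) = 51.2
- Additive: 80 × (1 − 0.20 − 0.20) = 48

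Either reproduces the stated 50. Expected dropouts: 80 × 0.20 = 16. The plan does not divide these 16 into not dosed, dosed but refusing assessment, and dosed but willing to be assessed. Only the last group is affected by this point.

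**4. What drives the bias**

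Let p be the share of an arm's dosed participants who stop and are not assessed. Let g be their mean outcome minus that of completers in the same arm, given baseline. The all-dosed arm mean is the completer mean + p·g. An analysis that sees only completers therefore misstates the arm difference by p(E2)·g(E2) − p(placebo)·g(placebo). The documents give neither p by arm nor g for SCR, BOLD or CAPS-5, so I put no number on it.

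**5. Whether the gain is power** (illustration only)

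Section 9.5 gives no effect size. Back-solving from 85% power with 25 per group, assuming a two-sided 0.05 test, gives d = (1.960 + 1.036) × √(2/25) = 0.848. This is an assumption, not a check on the plan. If all 16 dropouts attended and 20% of data were unusable, usable N = (64 + 16) × 0.8 = 64, against 51.2 with none attending. Power is Φ(d·√(n/2) − 1.960), with n per group and d diluted in proportion to the 16/80 stoppers:

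| Scenario | N | d | Power |
|---|---|---|---|
| None of the 16 attends | 51.2 | 0.848 | 86% |
| All attend, full effect in stoppers | 64 | 0.848 | 92% |
| All attend, half the effect | 64 | 0.763 | 86% |
| All attend, no effect | 64 | 0.678 | 77% |

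Power can move either way. The gain is measured outcomes for the stated analysis set and less reliance on the missing-data assumption.

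**The case against.** A reader might infer that the protocol cancels Visits 10-14 for anyone who stops, so that up to 16 dosed participants lack an endpoint by rule. The documents do not support that.

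- No section expressly cancels those visits. The final evaluation is undefined and could include a CAPS-5.
- Section 5.7 concerns withdrawal and termination, and 8.1 limits its rule to stopping both treatments. Someone who stops only capsules may be meant to stay on schedule.
- Sections 4.2.2 and 8.1 distinguish treatment from study or assessments. Section 8.1 promises safety assessments to all at 3 and 6 months. Section 11 asks staff to keep participants in the study through follow-up. Section 8.4.2 mentions follow-up after study drug is stopped for pregnancy.
- The 20% in Section 9.5 is dropout of every kind. Section 5.7.1 lists not wanting to continue among the reasons, so the number who stop treatment yet accept assessment is unknown and could be small.
- Section 9.4.6 plans sensitivity analyses and, if needed, methods for informative missingness.

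The first four stand as limits on what can be claimed, and the fourth rules out a count. They do not remove the point. Safety assessments are not outcome assessments, general retention language does not say which visits a stopper attends or when, and the sensitivity analyses, which are loosely specified, do not replace data that could have been collected.

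**Conclusion.** The point holds in limited form. Section 5.7.2 treats stopping study treatment as discontinuation from the trial, its final evaluation has no defined content or timing, and no text provides for outcome collection at Visits 10-14 afterwards, while the primary sample includes every dosed participant. Sections 5.7.2 and 8.1 disagree on the trigger and must be reconciled.

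The outer bound is the roughly 16 of 80 expected dropouts. The affected subgroup within it is not stated, so neither the number of lost outcomes nor the bias can be sized from the documents. The conclusion rests on sites applying 5.7.2 as written and on at least some stoppers being willing to be assessed. This is a cheap improvement to the plan; the documents do not show that the trial's result is compromised.

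**What to change.** Amend Sections 5.7.2 and 8.1 together:

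1. State that stopping capsules, PE or both does not by itself end outcome follow-up.
2. Invite the participant to the remaining outcome visits (10-14) at the times they would have fallen on her planned schedule, unless she declines assessments or the study clinicians decide under the existing text of 5.7.1 and 8.1 that participation should end.
3. Define the final evaluation. If she declines the experimental days, it is the existing Visit 12 battery, including CAPS-5 Past Week by the blinded evaluator.
4. Reconcile the two passages so that both sites apply one trigger.
5. Record treatment stop and withdrawal from assessments as separate items on the Early Withdrawal Form already listed in Section 7.2.6, so that analysts can tell them apart.

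No criterion for stopping treatment, and no existing scan-day safety requirement, is altered. The cost is a short amendment, matching consent wording and some extra contact effort. The visits, instruments and form already exist in the protocol.
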